Health-related quality of life. While single-item measures of pain level/relief are currently the most reliable and valid options to measure pain intensity,^{85,87} the multidimensional aspect of the pain experience has led consensus recommendations for use of "global" measures of improvement in chronic pain trials.⁷⁸ The Patient Global Impression of Change Scale is one such measure allowing patient evaluation of integrated treatment effects.⁷⁸ This measure is a 7-point ordinal scale requiring the subject to rate the current severity of their global

situation as it relates to phantom limb pain (as defined by each individual) compared to their baseline. This scale has the words "very much worse" to the left by the number one, and "very much improved" to the right, adjacent to the number seven. The words "no change" are in the middle of the scale above the number four. The Patient Global Impression of Change Scale has been validated in over ten prospective trials,⁷⁸ including studies specifically involving peripheral neuropathy.^{78,88}

Hypothesis 2b: Physical and emotional **functioning** will be significantly improved 4 weeks following an ambulatory CPNB (as measured with the Brief Pain Inventory).

It is well-recognized that, "pain is a complex, multidimensional, sensory, and emotional experience that is individually perceived and described in many different ways."^{85,87} This observation has led to consensus recommendations that "multiple core domains and related measures be considered in pain treatment trials,"⁸⁵ that "tap into a wider experience of pain over time and its impact on functioning and quality of life."⁸⁷ Therefore, the proposed trial will include the Brief Pain Inventory, an instrument that includes—in addition to pain intensity scales—seven measures evaluating pain's interference with physical and emotional functioning, such as sleep, relations with others, and enjoyment of life.^{82,83} The Brief Pain Inventory has been used in countless clinical studies of chronic pain,⁸² and validated specifically in neuropathic pain states.^{83,89-91} This instrument is associated with minimal subject burden and is easily interpreted by patients of all ages and education levels.⁸³ It has high test-retest reliability and correlates well with much longer questionnaires, including the McGill measures and EuroQol.⁸³

Hypothesis 2c: **Depression** will be significantly decreased 4 weeks following an ambulatory CPNB (as measured with the Beck Depression Inventory).

Multiple investigations demonstrate that factors such as anxiety and depression are strong predictors of pain intensity.^{92,93} Therefore, the proposed study will evaluate additional psychosocial factors using the Beck Depression Inventory.⁹⁴ This 21-item instrument measures characteristic symptoms and signs of depression, requires only a 5th grade comprehension level to adequately understand the questions, demonstrating high internal consistency (0.73-0.92, mean of 0.86), reliability and validity.^{95,96} Each of the 21 factors is rated on a 0-3 scale, and then summed to produce the total score of 0-63. Mild, moderate, and severe depression is defined with scores of 10-18, 19-29, and 30-63, respectively. While this instrument requires less than 10 minutes to complete, on average, it will be administered only at the initial baseline and four weeks following each perineural infusion (initial and crossover) to minimize subject burden and fatigue.

Additional pain-related data. Frequency and average duration of non-painful phantom sensations, phantom limb pain, and residual limb pain will be assessed.⁸³ In addition, supplemental analgesic use will be recorded, and other pain locations/severity will be evaluated using the NRS.⁸³ Lastly, to investigate masking adequacy, subjects will be queried four weeks following catheter insertion on the infusion type (active drug vs. placebo) they believe they received.

Data collection. Subject demographic and catheter insertion data will be uploaded from each enrolling center *via* the Internet to a secure,⁹⁷ password-protected, encrypted central server (Clinical and Translational Research Institute, University of California San Diego, San Diego, California).⁹⁸ The questionnaire for all subjects—regardless of enrolling center—will be administered by telephone from the University of California San Diego by research coordinators specifically trained in this instrument's application, minimizing inter-rater discordance. Staff masked to treatment group assignment will perform all assessments. This web-based data-collection protocol has been used successfully by the investigators for numerous previously published

Statistical Plan and Data Analysis

The randomized groups will be descriptively compared on baseline demographic and pain variables using descriptive statistics. In particular, groups will be considered well-balanced on a particular baseline variable if the standardized difference (difference in means or proportions divided by the pooled standard deviation) is less than $\sqrt{2/n}$, where *n* is the per-group sample size.¹⁰³ The primary analysis will be modified intention-to-treat, in which all randomized subjects who received any of the study treatment will be included and retained in their respective treatment groups.¹⁰⁴

Hypothesis 1: Primary outcome. We will assess the average causal effect of ambulatory CPNB versus placebo on phantom limb pain intensity (average pain over past 72 hours) at 4 weeks after the initial perineural catheter insertion and subsequent infusion using analysis of covariance to adjust for baseline pain intensity and any imbalanced baseline variables (see above). Results will be summarized as the least squares difference in means at 4 weeks and 95% confidence interval. Mean and standard deviation change from baseline intensity will also be summarized. Similar analyses will be conducted for the secondary outcomes of current/present, worst and least phantom pain, as well as average and worst residual limb pain.

Secondary outcomes.

Hypothesis 2a. The randomized groups will be compared on the global measure of improvement (Patient Global Impression of Change Scale) at 4 weeks using the Mann-Whitney test. Proportional odds logistic regression will be used to adjust for any imbalanced baseline variables, as appropriate.

Hypothesis 2b. The randomized groups will also be compared at 4 weeks on the seven measures of Brief Pain Inventory which evaluate pain's interference with physical and emotional functioning. We will use a mixed effects multivariate model (random subject term, fixed treatment effect, unstructured correlation matrix) to first assess whether the treatment effect differs across the 7 measures (i.e., treatment-measure interaction). In presence of an interaction, each measure will be evaluated univariably. Otherwise, an overall treatment effect will be estimated from the mixed effects model as the primary result for this aim.

Hypothesis 2c. Analysis of covariance adjusting for baseline score will be used to assess the treatment effect of ambulatory CPNB versus placebo on depression at 4 weeks after randomization as measured by the Beck Depression Inventory.

Blinding assessment. We will assess the quality of the blinding of subjects to initial treatment assignment by comparing the randomized groups on the proportion guessing correctly at 4 weeks (after measuring primary outcome pain scores) as to which group they were originally assigned; a Pearson's chi-square test will be used.

For all analyses, alternative statistical methods will be used if the assumptions of the planned analyses are not met. For instance, t-tests or regression analyses on the change or percent change from baseline (depending on which is less correlated with baseline score) will be used instead of analysis of covariance when comparing groups on the 4-week outcomes if the treatment group-by-baseline interaction is significant. Transformations of the data or Mann-Whitney test or other non-parametric procedures will be used if the assumptions of normality and/or equal variances are not met.

Crossover phase. Beginning 4-6 weeks after the original randomization, requesting subjects will receive the opposite treatment from that received in their original randomization, and the same measurements will be collected through 28 days (see Table 1). This option will allow all subjects the opportunity to receive the study treatment. Although a completely unbiased assessment of the average causal effect will not be possible for this

phase because the second treatment will be voluntary, and crossover will thus likely be requested more often from those receiving placebo in the first phase, we will still descriptively report the average treatment effect from those choosing to cross over (but no testing will be done; unbiased average causal effect will be obtained from the first phase).

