New imaging techniques such as functional magnetic resonance imaging have documented a correlation between phantom limb pain and cortical reorganization—with the most intense phantom pain provoking the greatest cortical changes.21 Amazingly, when the neural input from an amputated limb was blocked with a single injection of local anesthetic (a peripheral nerve block) in six patients, three had *immediate, complete* resolution of their phantom pain; and, within minutes the cortical abnormalities were corrected for these three individuals.²³ Unfortunately, when the single-injection nerve block resolved after a few hours, the phantom pain returned. But, this intriguing result demonstrates that the abnormal mapping—and phantom pain—that occur with amputation are not necessarily fixed, and may be dependent on signaling from the peripheral nervous system. Importantly, studies of chronic low back pain demonstrate that cortical thickness and cognitive abilities increased simultaneously 6 months after pain treatment.²⁴ These results demonstrate that chronic-pain-induced functional and structural brain abnormalities are not only reversible, but that treating chronic pain can restore normal brain function.²⁴ In other words, chronic phantom pain and cortical abnormalities may be maintained from abnormal peripheral input, suggesting that *a peripheral nerve block of* extended duration—lasting days rather than hours—may permanently reorganize cortical pain mapping, thus providing *lasting* relief from phantom pain.

Continuous peripheral nerve blocks. Until recently, extending a peripheral nerve block beyond 16 hours was unrealistic. However, a relatively novel treatment option—"perineural local anesthetic infusion", or a "continuous peripheral nerve block" (CPNB)—is now available (Figure 1). This technique involves the percutaneous insertion of a catheter directly adjacent to the peripheral nerves supplying the affected limb. Local anesthetic is then infused *via* the catheter(s) inducing a completely insensate extremity for as long as desired without any systemic side effects.²⁵

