amputation will be provided with crutches that they will be instructed to use until the day following catheter removal. Bathing will be permitted, as long as the catheter and infusion pump remain dry (e.g., sponge baths). Subjects will be discharged home with their portable infusion pump and perineural catheter *in situ*, and telephoned beginning the afternoon of catheter insertion and each subsequent day until catheter removal. During these calls, investigators will review gross sensory and motor function of the remaining limb; local anesthetic toxicity symptoms; infections signs and symptoms; catheter site appearance; infusion pump functioning (simply the volume infused displayed continuously and a flashing green light); and answer any questions.

With thorough catheter securing techniques such as catheter tunneling and others included in this protocol, the catheter dislodgement rate is less than 5% for infusions greater than one week, in both civilian⁷⁷ and military settings.⁶ However, inadvertent premature catheter dislodgement does rarely occur.³⁷ In the proposed study, if premature dislodgement occurs, the subject may opt to have the catheter replaced as soon as can be arranged with the investigators. All subjects will be retained in their respective treatment groups for analysis per the intent to treat principle.

Six days following catheter insertion, the study fluid reservoir(s) will be exhausted and subjects or their caretakers will remove the perineural catheter(s) with instructions given by an investigator *via* telephone. This procedure encompasses simply removing the occlusive dressing and gently pulling on the exposed perineural catheter. Home removal has been used successfully for tens-of-thousands of previous patients,^{31,37} and in one survey over 95% of patients responded that catheter removal was "easy" and that they would not have preferred to return for removal.³² However, if a subject desires, the patient may return to the medical center for catheter removal by a health-care provider.

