14. POTENTIAL RISKS

- 1. Infection. Since the catheter will be left in place for 6 days, there is a very small risk (<1%) of infection.
- 2. Falling. The risk of falling due to the perineural infusion in lower extremity amputees is currently unknown, since this intervention has not been prospectively investigated previously.
- 3. Catheter dislodgement. There is a risk of the catheter being accidentally and prematurely dislodged or becoming disconnected from the infusion pump.
- 4. Catheter retention (<0.01%)
- 5. Bleeding (<0.01%)
- 6. Nerve injury (<0.01%)
- 7. Local anesthetic toxicity (<0.01%)
- 8. Loss of confidentiality

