15. RISK MANAGEMENT PROCEDURES AND ADEQUACY OF RESOURCES

Planned procedures for protecting against or minimizing potential risks include:

During catheter placement, subjects will be continuously monitored with pulse oximetry, noninvasive blood pressure cuffs, and EKG (standard for catheter placement). Subjects will receive an IV so that emergency medications could be given, if needed. As described above, catheters will be placed under sterile conditions as is standard-of-care for any percutaneous catheter placement.

During the infusions, the subjects will be contacted through the day following catheter removal by an investigator or research coordinator, and subjects will have a physicians' pager and cellular phone numbers available to respond 24 hours/day and 7 days/week until the day following catheter removal. This procedure has proven effective for ambulatory surgical patients with perineural local anesthetic infusions. Patients will be called daily and asked about signs and symptoms of catheter infection. Should a catheter become infected, the catheter will be removed and oral antibiotics prescribed. Subjects with lower extremity infusions will be given crutches to use during the infusion itself.

If a catheter is accidentally and prematurely dislodged or disconnected from the infusion pump, the patient will turn off the infusion pump and may opt to have the catheter/pump replaced as soon as possible with the investigators.

The risks to confidentiality are the release of names/ telephone numbers/ demographic data (e.g. weight, age,

height), which will be minimized by the use of password-protected computers and case report forms that will be stored in locked offices. The study is triple-masked and placebo-controlled, so in case of a complication related to the delivery of study fluid, the investigational pharmacy will be contacted to determine study group. However, in case of a severe adverse event or medical emergency, the pump can be disabled, the tubing clamped shut, and/or the catheter removed—so that infusion may be stopped without knowing study group assignment.

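### Listed safety questions stop at catheter removal or the day after, so later nerve injury and infection are weakly ascertained, and nerve injury possibly unequally between arms

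*Combined protocol and SAP*

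**What the plan says.** Section 9 (Ambulatory infusion) has subjects "telephoned beginning the afternoon of catheter insertion and each subsequent day until catheter removal". In these calls "investigators will review gross sensory and motor function of the remaining limb; local anesthetic toxicity symptoms; infections signs and symptoms; catheter site appearance", together with pump function. Catheters come out at home on Day 6, with a return visit only if the subject wants one.

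Section 15 sets a different end point: "the subjects will be contacted through the day following catheter removal by an investigator or research coordinator". The only question it names is infection: "Patients will be called daily and asked about signs and symptoms of catheter infection". The physicians' pager and telephone numbers are "available to respond 24 hours/day and 7 days/week until the day following catheter removal".

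Section 7 describes the technique as "inducing a completely insensate extremity for as long as desired". Section 14 lists infection (below 1%) and nerve injury (below 0.01%) among the risks.

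Central telephone questionnaires continue on Days 7, 14, 21 and 28 and at 6 and 12 months (section 9, Outcome measurements and Table 1). Their listed content is phantom and residual limb pain, pain interference, global impression of change, depression, phantom sensations, analgesic use, pain elsewhere and a masking question. The Day 7 to 28 calls are repeated after an optional crossover infusion.

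Sections 15 and 18 tell subjects to call an investigator with concerns and provide for adverse-event reporting to the IRB. The medical monitor and DSMB review adverse events (section 9, Study Design). The statistical plan describes no safety analysis.

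**The concern.** Two named risks are actively looked for mainly while the catheter is in place. For nerve injury this is the least informative time in the active arm, because numbness or weakness during a ropivacaine infusion may simply be the intended block. In the saline arm only the initial lidocaine has to wear off, after which the same question can separate a normal limb from an abnormal one. A comparison of sensory or motor complaints between arms, built from these calls, would not compare like with like.

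For infection the difficulty is timing, not arm: both arms are asked the same questions while the catheter is in, and neither has a listed question after removal or the day following.

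At stake is what the medical monitor, the DSMB and the final report can say about harm. Contact with subjects is not lost. The later calls are made, but no safety question is listed for them.

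**Working it through.** **When the daily calls end.** Section 9 gives 1,100 mL of study fluid at 7.5 mL/h (lower limb: 2.5 + 5 = 7.5 mL/h). 1,100 / 7.5 = 146.7 h, and 146.7 / 24 = 6.1 days. This reproduces the plan's six days, so removal on Day 6 is consistent.

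**What is asked, and when.**

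| Contact | Window | Listed safety content |
|---|---|---|
| Daily calls, section 9 | Day 0 to removal (Day 6) | Sensation, movement, toxicity, infection, site, pump |
| Daily contact, section 15 | To the day after removal (Day 7) | Infection |
| Questionnaire calls, section 9 | Days 1, 7, 14, 21, 28; months 6, 12 | None listed |

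**Time without a listed safety question, to Day 28.**
- Section 9 reading: 28 − 6 = 22 days; 22/28 = 79%.
- Section 15 reading: 28 − 7 = 21 days; 21/28 = 75%.

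**Calls at which a nerve deficit could be recognised.** Day 0 plus Days 1 to 6 makes 7 calls under section 9. The documents do not say how long the lidocaine lasts, so this is an assumption. If it has worn off by the Day 1 call, 6 calls are interpretable in a saline subject; if only by Day 2, 5 are. In a ropivacaine subject the number is 0 if the infusion keeps the limb numb throughout, as section 7 describes, and higher if the study rates leave sensation partly intact. Section 15 adds one contact after the infusion has ended, but lists no sensory or motor question for it.

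Staff are masked, so during the infusion a caller cannot tell block from injury in either arm. The difference between arms appears when results are tabulated by treatment. After the infusion and the block have ended, the same question has the same meaning in both arms.

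**What the trial could show with complete ascertainment.**
- One-sided 95% upper bound after zero events in n subjects: 1 − 0.05^(1/n). For n = 72 (maximum per arm): 1 − 0.05^(1/72) = 4.1%.
- Chance of at least one nerve injury at a rate of 0.01%: 1 − 0.9999^72 = 0.7% in 72 subjects; 1 − 0.9999^180 = 1.8% in the 180 whom section 10 expects to enrol.
- Infections at the 1% ceiling: 0.01 × 180 = 1.8 after first infusions, and 3.6 if every subject crossed over. These are upper limits on all infections, not on missed ones. The documents give no late fraction, and section 9 does not expect universal crossover.

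**The case against.** The strongest reply is that detection is thin after removal but not absent.

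- Section 15's next-day contact and the Day 7 questionnaire call both follow the end of infusion, and a deficit could be raised at either.
- Subjects are told to call with any concern, with no end date on that instruction, although the 24-hour cover does end.
- Residual limb pain is recorded at Day 28 and at 6 and 12 months, and interference items, global change and pain elsewhere could reflect a painful nerve injury.
- A ropivacaine-first subject who crosses over is seen again, tested for cold sensation after the lidocaine injection, and then called daily on saline.
- The claim of a fully insensate limb comes from the background. The catheter success test requires only reduced cold sensation, and nothing shows that every limb stays numb at the study rates.
- The case report forms are not among the documents, and the later call content is described under an outcomes heading.

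All of this stands, and it rules out two stronger readings that a reader might infer: that nerve injury cannot be assessed at all under ropivacaine, and that the DSMB's adverse-event table would be clean by construction. Infection is asked about daily in both arms during the infusion, so the arm-inequality argument does not extend to it. Section 14 also does not attribute nerve injury to the drug; needle or catheter injury could occur in either arm.

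None of this supplies a planned question after the infusion. The pain items are non-specific and would miss painless numbness or weakness, crossover is optional, and subject-initiated reporting is passive.

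**Conclusion.** The concern holds in limited form. Sections 9 and 15 disagree on when daily contact ends and what it covers, and must be reconciled. On either reading the only listed sensory and motor checks fall during the infusion, and 21 to 22 of the 28 days to the primary endpoint have no listed adverse-event, neurologic or infection question. Ascertainment of nerve injury and late infection is weak and, for nerve injury, potentially unequal between arms.

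The inequality rests on two assumptions that the documents do not quantify: that ropivacaine at the study rates keeps the limb numb enough to hide a deficit, and that the lidocaine wears off early in the infusion. The gap in later questions depends on neither. It does assume that unseen case report forms do not already ask them.

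A reader might also infer that better questions would let the trial state a nerve-injury rate. They would not: with 72 subjects per arm, zero events excludes only rates above about 4.1%, far above the stated figure of below 0.01%. The gain is in detection and in comparability between arms. This is a worthwhile, inexpensive improvement; the primary efficacy analysis is unaffected.

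**What to change.** Add a short fixed adverse-event script to the existing Day 7, 14, 21 and 28 calls after each infusion, and to the 6-month call. Ask about new numbness or weakness compared with before insertion; redness or drainage at the site, or fever; and any care sought. Put it after the pain questions so that it cannot colour the primary outcome. Pass positive answers to the site investigator. State in the statistical plan that the answers will be tabulated by solution received in each infusion, for the medical monitor and DSMB.

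Reconcile sections 9 and 15 on when daily contact ends and which questions it includes. If the case report forms already carry such questions, a sentence saying so would cover the content of the later calls. Describe any projected infection count as an upper limit on all infections, or leave it out.

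The cost is protocol wording, one or two more minutes per call, and more minor events to record and report. No new visit, call or staff is needed, and masking is preserved.

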Randomization will be stratified by institution/hospital and amputation location (upper vs. lower limb) in a 1:1 ratio, and in randomly chosen block sizes. Randomization lists will be created using Statistical Analysis Software computer-generated tables by the University of California San Diego Investigational Drug Service. A randomization list for each enrolling center will be created by the University of California San Diego Investigational Drug Service, and uploaded to a secure, password-protected, encrypted central server. Investigational pharmacists at each institution will prepare all study solution as determined by these randomization lists, accessed by the pharmacists *via* the web-based, secure, password-protected, encrypted central server. Ropivacaine and normal saline are indistinguishable in appearance, and therefore investigators, subjects, and all clinical staff will be masked to treatment group assignment. Unmasking will not occur until statistical analysis is complete (termed "triple masking": subjects, investigators, and statisticians).

Study intervention. Electronic, programmable, portable infusion pumps will be used to administer perineural study solution at fixed rates for over 6 days.³⁶ Electronic, programmable, portable infusion pumps are currently used by the United States Armed Forces and have been used previously by the military to provide CPNB for up to 27 days immediately following limb trauma in soldiers returning from Iraq and Afghanistan.²⁵ Subjects will receive a total of 1,100 mL of study fluid from either one (upper extremity) or two (lower extremity) pump and external reservoir combinations. The continuous basal infusion rate will be determined by catheter location: femoral 2.5 mL/h; popliteal-sciatic 5 mL/h; and infraclavicular 7.5 mL/h (37.5 mg/h for both upper and lower extremity subjects). No patient-controlled bolus dose will be included.

Ambulatory infusion. Prior to discharge, subjects and their caretakers will be provided with verbal and written catheter/pump instructions, the telephone and pager numbers of an investigator available at all times, and a copy of the Institutional Review Board-approved consent form. Subjects with a lower extremity

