Interim analyses. We will conduct interim analyses to assess efficacy (rejecting null) and futility (rejecting alternative) at each 25% of the maximum enrollment using a group sequential procedure. Specifically, a gamma spending function will be used with parameters -4 and -2 for efficacy and futility, respectively.¹⁰⁵ Thus, boundaries at the 1st through 4th analyses for efficacy (futility in parentheses) will be P \leq 0.0016 (P>0.9572), P \leq 0.0048 (P>0.7186), P \leq 0.0147 (P>0.2389) and P \leq 0.0440 (P>0.0440), Figures 7 and 8.

Figure 7. Boundaries for efficacy and futility.

Figure 8. Alpha and beta spending functions

Type I error. We will use a parallel gatekeeping procedure to control the study-wide type I error at 0.05.¹⁰⁶ For this procedure we therefore a priori prioritize the study outcomes into ordered sets, as Aim 1, Aim 2a, Aim 2b and then Aim 2c. Analysis will proceed in that order, and testing will proceed through each "gate" to the next set if and only if at least one outcome in the current set reaches significance. The significance level for each set will be 0.05 times a cumulative penalty for non-significant results in previous sets (i.e., a "rejection gain factor" equal to the cumulative product of the proportion of significant tests across the preceding sets). Within a set, a multiple comparison procedure (Bonferroni correction) will be used as appropriate to control the type I error at the appropriate level. SAS statistical software (Carey, North Carolina), R programming language (The R Project for Statistical Computing) and East 5.3 software (Cytel Inc.) will be used for all analyses.

Sample size considerations. Our sample size estimate is based on the primary specific aim of whether the addition of an ambulatory CPNB decreases phantom limb pain intensity resulting from a traumatic amputation compared with current standard-of-care treatment at 4 weeks following the ambulatory CPNB. Receiver operating characteristic curve analyses demonstrate that changes from baseline of at least 1.7 along a 10-point NRS accurately identified patients who rated improvements as "much improved" or more, compared with those who perceived no change or worsening following analgesic interventions.⁸⁸ Multiple additional studies confirm this degree of reduction as clinically meaningful to individual patients with chronic pain.^{85,107,108}

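### The primary ANCOVA leaves out the randomisation strata, and the alternative-methods clause can displace its adjusted NRS-point difference as the primary result

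*Combined protocol and SAP*

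**What the plan says.** All references are to Section 9 unless stated.

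- **Treatment group assignment:** "Randomization will be stratified by institution/hospital and amputation location (upper vs. lower limb) in a 1:1 ratio".
- **Hypothesis 1 (primary outcome):** the 4-week average pain score is compared "using analysis of covariance to adjust for baseline pain intensity and any imbalanced baseline variables (see above"). Site and limb are not named here, and no other section adds them.
- **Imbalance rule (opening of the statistical plan):** "groups will be considered well-balanced on a particular baseline variable if the standardized difference" is below the square root of 2/n, with n the per-group size.
- **Reporting of the primary outcome:** "Results will be summarized as the least squares difference in means at 4 weeks and 95% confidence interval". The next sentence adds the mean and SD of change from baseline, without conditions.
- **Alternative methods (after the blinding assessment, covering all analyses):** if the treatment-by-baseline interaction is significant, analyses of "change or percent change from baseline (depending on which is less correlated with baseline score) will be used instead of analysis of covariance". In addition, "Transformations of the data or Mann-Whitney test or other non-parametric procedures will be used if the assumptions of normality" or equal variance fail. No level is given for the interaction test, and no test or level for normality or variance.
- **Interim analyses:** "We will conduct interim analyses to assess efficacy (rejecting null) and futility (rejecting alternative) at each 25% of the maximum enrollment". The primary model is therefore used up to four times.

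**The concern.** There are two separate mismatches.

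**Design and analysis.** Stratified blocking removes site and limb differences from the treatment comparison. A model without those factors still counts their variation as residual noise. Its standard error is then too large whenever they are prognostic. The cost would be a conservative test and fewer early efficacy stops.

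**Promise and fallback.** The trial is powered on 1.7 NRS points and promises an adjusted difference in those units. A data-dependent clause with unstated trigger levels can substitute another scale. The interaction trigger fires most often when benefit grows with baseline pain, which is plausible on a 0-10 scale with entry at 2, and the substitute test can then be less powerful than the one it replaces.

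**Working it through.** **1. Reproduce the plan's design.** Inputs from Sample size considerations and Interim analyses: effect 1.7, SD 3.0, correlation 0.50, two-sided 0.05, power 0.90, and four looks at P bounds 0.0016/0.0048/0.0147/0.0440.

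- SD of change = 3.0 × √(2 × (1 − 0.50)) = 3.0.
- Simulated paths at N=144 give power 0.901. Crossing probabilities under the alternative are 0.083/0.291/0.379/0.247 (Table 2: 0.083/0.290/0.379/0.248). Expected N is 100.5 and 102.4 (stated 100 and 102). The design reproduces.
- ANCOVA residual SD = 3.0 × √(1 − 0.25) = 2.598 (variance 6.75), which gives power of about 0.96. The planned analysis has reserve.

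**2. Can the imbalance rule bring the strata in?** The standard error of a standardised difference is √(1/n + 1/n) = √(2/n), so the threshold is one standard error (0.167 at n = 72).

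- An unstratified variable is flagged by chance with probability 2 × (1 − Φ(1)) = 0.317.
- Under stratified blocking (assumed sites of 48/24/24/24/24, 85% lower limb, blocks of 2/4/6), each site indicator was flagged in under 0.1% of simulated trials and limb in about 3%.
- With blocks of 2 or 4 and 20% upper limb, limb was flagged in about 12/4/1/0.3% at looks 1 to 4.

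**3. Direction of the effect.** If the strata explain a share s of residual variance, the true variance of the estimate is about (1 − s) times what the model reports. The single-look error at nominal 0.05 is then about 2 × (1 − Φ(1.96/√(1 − s))).

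- s = 0.10: 1.96/0.949 = 2.066, error about 0.039 (simulated 0.040).
- s = 0.20: 1.96/0.894 = 2.191, error about 0.028 (simulated 0.032).

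**4. Four looks.** Ranges span two simulations of the plan's boundaries, with futility ignored. The 5% row comes from one of them. That one assumes one third of patients at the largest site (60 of 180, Section 10), one sixth at each other site, 20% upper limb, and strata variance split equally between site and limb.

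| Strata share (assumed) | Type I error, baseline only | Type I error, with strata | Efficacy by 72 patients, baseline only | Efficacy by 72 patients, with strata |
|---|---|---|---|---|
| 0% | 0.053 | 0.052-0.054 | 0.43-0.47 | 0.43-0.45 |
| 5% | 0.046 | 0.053 | 0.44 | 0.47 |
| 10% | 0.035-0.042 | 0.045-0.054 | 0.44 | 0.49-0.50 |
| 20% | 0.024-0.030 | 0.046-0.052 | 0.44-0.45 | 0.56-0.57 |

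Mean N at effect 1.7, with both boundaries applied, moves from 94.7 to 95.4 at 0%, from 94.1 to 90.8 at 10%, and from 94.4 to 86.8 at 20%. Overall power is at least 0.966 in both models.

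**5. The interaction fallback.** Assumptions: integer 0-10 scores; interaction level 0.05; then whichever of change and percent change is less correlated with baseline. Three baseline settings were used: mean 5, SD 2, with minimum 1 or 2; and mean 6, SD 1.5, minimum 2.

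- *No effect:* error 0.050, against 0.049 with ANCOVA locked.
- *Constant effect:* about 4% of trials end on another scale; power loss 0.00-0.01.
- *Effect proportional to baseline:* 12-34% end on percent change. Power is about 0.88-0.95 by setting, against 0.96-0.97 locked. The largest loss is 0.964 − 0.878 = 0.086 and the smallest about 0.97 − 0.95 = 0.02.

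Percent change also asks a different question: 1.7 points is 85% of a baseline of 2 (the entry minimum in Section 10), 28% of 6 and 17% of 10. A Mann-Whitney test gives no difference in means.

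The normality and variance trigger cannot be sized from the documents, because the plan names no test. As illustration only, Shapiro-Wilk and Levene checks at 0.01 to 0.05, added to the interaction trigger, moved 13-35% of constant-effect trials to percent change or ranks.

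**The case against.** **Strata.** The documents give no prognostic value for site or limb. Questionnaires are "administered by telephone from the University of California San Diego by research coordinators specifically trained", which limits rater-driven site differences and points to the low end of the range. At a 5% share the saving is only 94.2 − 92.8 = 1.4 patients. This stands: the gain is conditional and may be near zero.

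**Imbalance rule.** It is prespecified and never uses the outcome. A reader might infer that admitting chance-flagged covariates inflates error. It does not, and the rule is a minor matter.

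**Fallback.** A reader might infer that the trial could end with no result in NRS points. The documents do not support that: mean and SD change are promised unconditionally, and the absolute-change route stays in NRS points. What can be lost is the adjusted difference with its interval as the primary result. A reader might also infer that choosing a method from the data inflates type I error. The null simulations show no such effect, and the statisticians stay masked until analysis is complete, which limits choice by direction of result. Finally, the larger power losses come from particular baseline distributions; with mean 6 and SD 1.5 the loss is about 0.02.

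These points lower the severity. They do not remove the mismatch between stratified allocation and unstratified analysis, or the unstated triggers for changing the primary scale.

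**Conclusion.** The concern holds in both parts, as something that should be changed rather than as a threat to validity.

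Omitting the strata leaves an unbiased test. It is conservative, and less likely to stop early for efficacy, only to the extent that site or limb is prognostic; the sizes above rest on assumed shares of 10% and 20%. It would be wrong to conclude that the omission biases the estimate, inflates error or undermines N=144.

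The fallback clause can displace the promised adjusted NRS-point difference. With the interaction tested at an assumed 0.05, the power cost is about 0.02-0.09 if benefit is proportional to baseline pain and 0.01 or less if it is constant. The mismatch in the text is certain. The magnitudes depend on assumed strata shares, trigger level and baseline distribution, none of which the documents give.

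**What to change.** Before the first look, specify one primary model for all four looks: Day-28 average NRS = treatment + baseline average NRS + limb + enrolling site, with model-based standard errors and a t reference on the residual degrees of freedom.

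- Use one term per site that has enrolled, or one site grouping fixed before the first look, masked to arm and kept throughout. This wording also copes with Section 9 listing five centers while Section 11 refers to four approved enrolling institutions.
- Keep the model's NRS-point difference and 95% CI as the primary result whatever the diagnostics show.
- Make the imbalance-adjusted, change, percent-change, transformed and rank analyses labelled sensitivity analyses. If an assumption check is kept, name its test and level and let it lead only to one of these.
- Report any treatment-by-baseline interaction as a supplement, in NRS points at stated baseline values.

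Cost: SAP wording and up to five degrees of freedom (limb 1, site 4). N does not change. If the strata are not prognostic, the chance of crossing the efficacy boundary by 72 patients falls by about 0.01 (0.434 to 0.427 in one simulation, 0.47 to 0.45 in the other).
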